Aim 1: Examine the immediate post-intervention effect of CHAMP (compared to control participants) on MC, PMC, and PA in preschool-age children.

The immediate post-intervention effect of CHAMP (compared to control participants) on each outcome variable will be evaluated at post-intervention (month 9). We will examine descriptive statistics on both pre- and post-intervention measures of the outcome variables for each group. The change of MC, PMC, and PA (i.e., PA refers to time spent in MVPA) will be compared between two groups using regression models, adjusting for other confounding factors. Random effects will be included in the model to accommodate for the potential within-cluster correlation coming from the nature of how the data are collected. We will also investigate the amount of attrition from pre-intervention to post-intervention, and attempt to identify baseline (or pre-intervention) predictors of the likelihood of dropping out (as an indication of possible bias in the change estimates).

Aim 2: Assess the sustainable effect of CHAMP (compared to control) on MC, PMC, and PA across middle childhood.

We will use MMR to analyze the clustered longitudinal data from our RCT to assess the long-term effects of the CHAMP intervention on improving the three (3) outcome measures, MC, PMC, and PA. In this analysis, we can obtain the estimates of the long-term longitudinal intervention effect, by adjusting for confounding factors (i.e., sex). For PA, we will test for a possible delay before any significant change because of the difficulty of achieving health behavior change by adding time-lagged covariates related to behavior changes in the regression analysis. We will also conduct exploratory analyses to test interaction effects to understand potential modified intervention effects by different levels of behavior changes. The intervention is designed to promote a positive trajectory of children's MC, PMC, and PA, and we will specifically test interactions between intervention and time, and between baseline motor skill and time, to see which baseline measure is a stronger driver of increasing physical activity.

Aim 3: Examine and compare the immediate and long-term mediating effect of PMC on the relationship between MC and PA in preschool-age children in the CHAMP and control.

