Missing Data: Assuming data are Missing at Random (MAR), multiple imputation techniques will be used to replace missing data.⁷⁶ Missing data will be assumed to be MAR if no participant demographics or primary outcomes are correlated with missingness. Mixed effects models allow for partial information to be included for individuals who may dropout prior to any post-intervention data collections. Sensitivity analysis over a range of missing data mechanisms will be performed as necessary. We expect limited missing data because the Michigan research staff will be present to supervise data collection and identify potential problems with missed data. Missing values will be multiply imputed using available covariates by sequential imputation. This approach allows optimal use of available data in analysis involving change measures.

Early Withdrawal/Dropouts: Measures will be taken to retain all participants overtime, however we do expect to loss participants in both the intervention and control groups overtime. A conservative estimate of this attrition rate is 30% during the study period. We plan to implement the intent-to-treat (ITT) analysis.⁷⁷ We will make every effort to collect follow-up data at each time point from individuals who have not withdrawn from the study. Our approach has been to sponsor booster sessions as “classroom reunion/birthday parties” along with rewards and incentives to gather follow-up data. This approach has worked well for bringing kids together to reduce potential dropout.

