More specifically, in Aim 1, the immediate post-intervention effect of CHAMP (compared with control participants) on each outcome variable will be evaluated at post-intervention (Month 9). We will examine descriptive statistics on both pre-intervention and post-intervention measures of the outcome variables for each group. The change in motor performance, perceived physical competence and physical activity (ie, physical activity refers to time spent in MVPA) will be compared between two groups using regression models, adjusting for other confounding factors (eg, age and sex). Random effects will be included in the model to accommodate the potential within-cluster correlation coming from the nature of how the data are collected. We will investigate the amount of attrition from pre-intervention to post-intervention, and attempt to identify the baseline predictors of the likelihood of dropping out (as an indication of possible bias in the change estimates).

In Aim 2, we will use Mixed Model Regression to analyse the clustered longitudinal data from our RCT to assess the long-term effects of the CHAMP intervention on improving the three outcome measures: motor performance, perceived physical competence and physical activity. In this analysis, we can obtain the estimates of the long-term longitudinal intervention effect by adjusting for confounding factors that include sex and age. For physical activity and BMI, we will test for a possible delay before any significant change because of the difficulty of achieving health behaviour change by adding time-lagged covariates related to behaviour changes in the regression analysis. We will also conduct exploratory analyses to test interaction effects to understand potential modified intervention effects by different levels of behaviour changes. The intervention is designed to promote a positive trajectory of children's motor performance, perceived physical competence, and physical activity, and we will specifically test interactions between intervention and time and between baseline motor skills, perceived physical competence, and time to see which baseline measure is a stronger driver of increasing physical activity.

In Aim 3, we will apply the Growth Curve Models to understand if, and how, time-course changes in motor performance, perceived physical competence and physical activity differ between the intervention and control groups. This model is also used to determine a time

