window over which the intervention effect appears stronger. We will use Structural Equation Models to determine which hypothesised constructs might be responsible for the intervention effect on longitudinal physical activity. Based on the results of our previous work, for example, we hypothesise that perceived physical competence will not mediate the relationship between motor performance and physical activity at baseline, but perceived physical competence will mediate the relationship between motor performance and physical activity immediately post-intervention and across the 3-year follow-up period. We will use Mplus software to fit Structural Equation Models, and the goodness of fit of Structural Equation Models will be assessed using multiple criteria such as χ^2 to df ratio (<2) and the root mean square error of approximation (<0.05).

Our goal is to have limited missing data but there is a potential for missing data. Assuming that data are missing at random, multiple imputation techniques will be used to replace missing data.⁹⁷ Missing data will be assumed to be missing at random if no participant demographics or primary outcomes are correlated with missingness. Mixed-effects models allow for partial information to be included for individuals who may dropout before any post-intervention data collection periods. Missing values will be multiply imputed using available covariates by sequential imputation. This approach allows optimal use of the available data in analysis involving change measures.

Data management

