Specific analysis plan for Aim 1. Examine the immediate (pre- to post-test) intervention effects of CHAMP (compared to control participants) on cognitive SR (cognitive flexibility, working memory, attention shifting), behavioral SR (behavioral inhibition), and emotional SR (emotion regulation). The immediate post-intervention effect of CHAMP (compared to control participants) on each SR outcome variable will be evaluated at post-intervention. We will examine descriptive statistics for both pre-and post-intervention SR outcome variables for each group. The change in cognitive SR, behavioral SR, and emotional SR scores will be compared between the intervention (CHAMP) and control groups using regression models, adjusting for other confounding factors. We assume randomization will be successful and we will monitor throughout the trial. It is always good practice to monitor along the way and we will do so, but randomization may be imperfect as this is a randomized cluster trial taking place in the real world (i.e., Head Start setting). If randomization does not work this will lead to biased results and methodology, our planned analyses to adjust other variables will be considered. Random effects will be included in the model to accommodate for the potential within-cluster correlations due to nested classroom data. We anticipate that some children will have only partial adherence to the intervention (i.e., attend a subset of sessions), thus we will also conduct a dose-response analysis where dose corresponds to number of sessions. We will investigate the amount of attrition from pre-to post-intervention, and attempt to identify baseline (or pre-intervention) predictors of dropping out. The information will indicate possible bias in the change estimates.

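### The attrition check and the missing-at-random rule do not say that dropout will be compared by arm, so they can miss, or falsely signal, bias in the CHAMP-versus-control contrast

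*SAP*

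**What the plan says.** Aim 1 compares change in motor competence, perceived competence and MVPA between the two arms. On attrition, the Aim 1 paragraph of the SAP (Analyses of primary outcomes) says "We will investigate the amount of attrition from pre-intervention to post-intervention" and that the team will "attempt to identify the baseline predictors of the likelihood of dropping out (as an indication of possible bias in the change estimates". Protocol section E, Objective 1, Aim 1 has "attempt to identify baseline (or pre-intervention) predictors of the likelihood of dropping out (as an indication of possible bias in the change estimates", and Objective 2, Aim 1 repeats it. The self-regulation part of the SAP (Specific analysis plan for Aim 1) has "attempt to identify baseline (or pre-intervention) predictors of dropping out. The information will indicate possible bias in the change estimates".

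The same SAP paragraph asks for descriptive statistics for each group, but the attrition sentence has no such qualifier.

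The neighbouring provisions do not bring arm in either:

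- **Missing-at-random rule** (SAP, and protocol Missing Data): "Missing data will be assumed to be missing at random if no participant demographics or primary outcomes are correlated with missingness". Arm is not listed.
- **Imputation:** sequential, from available covariates, which are not listed.
- **Adjustment in Aim 1:** "adjusting for other confounding factors (eg, age and sex". The baseline value of the outcome is not named.
- **Sensitivity analysis** (protocol only): "Sensitivity analysis over a range of missing data mechanisms will be performed as necessary".
- **Expected losses** (protocol, Early Withdrawal/Dropouts): "we do expect to loss participants in both the intervention and control groups overtime". Rates by arm are not given.

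**The concern.** The estimate at risk is a difference between arms. Dropout that depends on baseline in the same way in both arms shifts the change within each arm by a similar amount, and the shifts cancel in the difference. Dropout that depends on baseline differently by arm leaves groups with different baseline means. A comparison of raw change then picks up regression to the mean as if it were an intervention effect.

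A search for baseline predictors in the pooled sample does not separate these two situations. It can react strongly to the first. If the slopes oppose each other in the second, they average out and it stays silent. At stake is how the primary MVPA result is read: false reassurance, or needless doubt. The imputation model is also at stake, since nothing says that arm belongs in it.

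**Working it through.** **Inputs from the protocol (Sample Size, Power Analysis and Sample Attrition).** Target difference 12.1 min/day, SD 27, alpha 0.05, power 90%, 106 per arm analysed, 30% loss, 298 recruited.

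**The plan's own figure.** n per arm = 2(1.96 + 1.282)² × 27² / 12.1² = 104.7, so 105 by the normal formula. The t-test version gives 105.6, so 106, which reproduces the plan. Dividing by 0.7 gives 152 per arm (304 in total), close to the stated 298. The plan gives no figure for the attrition check itself.

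**Assumptions not in the documents.** Baseline-to-post correlation r = 0.5; SD 27 for levels; no clustering; log-odds slopes of dropout per baseline SD as shown; each check read at p < 0.05; 150 children per arm. With r = 0.5 the SD of change is 27 × √(2 × (1 − 0.5)) = 27, so the level SD agrees with the planning SD.

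**Mechanism.** If the remaining CHAMP children differ from the remaining controls by Δ baseline SDs, raw change is biased by −(1 − r) × 27 × Δ = −13.5 Δ min/day. A bias of 4.0 therefore needs Δ of about −0.30, and 7.0 needs about −0.52.

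**Simulation.** 1,000 trials per setting, true effect 0, complete cases, change not adjusted for baseline. Repeat runs differ by a few tenths of a minute.

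| Dropout pattern | Bias, min/day | Baseline-only check fires | Arm-by-baseline term fires |
|---|---|---|---|
| Same slope 0.5 in both arms, 30% | about 0 | 96% | about 5% |
| Opposite slopes 0.5 / 0.7 / 1.0, 30% | 4.0 / 5.2 / 7.0 | about 5% | 97–100% |
| Opposite slopes 0.5 / 0.7 / 1.0, 15% | 1.9 / 2.7 / 3.8 | 4–8% | 86–100% |
| Slope in CHAMP only, 0.5 to 1.0, 30% | 1.8 to 3.2 | 48–92% | 45–95% |

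Against the target, the second row is 4.0/12.1 = 33%, 5.2/12.1 = 43% and 7.0/12.1 = 58%. The direction depends on which arm loses its more active children.

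**What removes it.** In the opposite-slope and one-arm settings, adjusting for baseline MVPA brings the bias to about 0. In the opposite-slope settings, imputing from baseline and arm does the same (between −0.2 and 0.1).

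**What imputation without arm does.** Imputed children then contribute almost no arm difference, so a true effect shrinks by roughly the imputed share: 0.30 × 12.1 = 3.6 min/day. Simulated losses across these settings are about 3.5 to 4.4 min/day.

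**What a baseline check cannot see.** These settings use a true effect of 12.1 and slopes of 0.3 to 0.7.

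- Dropout of 20% versus 40% driven by an unobserved prognostic factor biases the contrast by 1.3 to 2.9 min/day in size. The baseline-only check fires about 5% of the time; an arm term fires 97%.
- An unobserved driver in one arm at equal rates gives 2.0 to 4.5 min/day, and every check, with or without arm, fires only about 5% of the time.
- Rates of 20% versus 40% unrelated to outcome give no bias.

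**The case against.** The strongest reply is that the plan does not exclude arm. It gives one sentence, with no model, covariate list or threshold, and a competent analyst may well include arm. The baseline-only check simulated here is therefore a literal reading, not a specified procedure. That stands, and the point is about what the text fails to commit to.

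Second, opposite slopes of equal strength are a worst case, and nothing in the documents makes them likely. The protocol expects losses from relocation and disinterest. With a slope in one arm only, the baseline-only check detects it about as often as the interaction term. That also stands.

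Third, the minutes of bias belong to an unadjusted complete-case contrast, whereas the plan promises multiple imputation, mixed models using partial data, and intention to treat. This largely stands, but only if baseline and arm enter the model, and the plan names neither.

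Fourth, the text speaks of change estimates, and within-arm change is indeed shifted (about 2.6 min/day at a common slope of 0.7). If the effect varies with baseline (by 50% per SD in one run), even a common pattern moves the contrast by about 1.3 min/day. A flag is then not false, and the plan attaches no decision to it.

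Fifth, 30% is described under Data Collection as a three-year figure, and the self-regulation supplement expects 16.5% by post-intervention. The sample-size section nevertheless applies 30% to the primary endpoint, so both rates are shown.

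A reader might also infer that this check is the plan's only guard against attrition bias. The documents do not support that. The missing-at-random rule and the protocol's sensitivity analysis are further guards, and CONSORT reporting is promised in the self-regulation section. None of them specifies whether predictors of dropout differ by arm.

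**Conclusion.** The gap is real and minor. Neither the attrition check nor the missing-at-random rule commits to comparing dropout by arm or to examining arm-by-baseline terms. Read literally, the check can give a false alarm about the contrast and can miss differential dropout.

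Under the stated assumptions the missed bias is about 4 to 7 min/day at 30% dropout and 2 to 4 at 15%, in the worst case only. It is about 2 to 3 min/day at 30% with a slope in one arm, and about 0 once the baseline outcome is adjusted for or imputation uses baseline and arm.

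It would be tempting to conclude that the primary estimate will be biased by up to 58% of its target, or that the check always fails when dropout differs by arm. The documents do not support either: arm is not ruled out, the final model is not fully specified, and a difference in dropout rate alone causes no bias.

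**What to change.** In Aim 1 of the SAP (main and self-regulation sections) and in protocol section E (Objectives 1 and 2, Aim 1):

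1. Report the amount of attrition, and reasons where known, by arm.
2. Model dropout on arm, the baseline outcome, age, sex and arm-by-baseline-outcome terms, with a random effect for class. Give estimates with confidence intervals, and read the arm and arm-by-baseline terms as the indication of possible bias in the group difference.
3. Add arm to the missing-at-random rule, and state that the imputation model includes arm and the baseline outcome.
4. Adjust the Aim 1 change model for the baseline outcome.
5. Replace sensitivity analysis as necessary with at least one named scenario in which missingness departs from missing at random differently by arm, since no baseline check sees an unobserved driver acting in one arm at equal rates.

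The cost is wording and a few model terms; no new data are needed and the sample size does not change. The interaction terms have limited power when dropout is low or slopes are modest (about 22% for a slope of 0.3 in one arm at 30% dropout), so a non-significant test should not be read as absence of bias.

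### Aim 2's test for a delayed effect on physical activity and BMI conditions on behaviour measured after randomisation, so its arm coefficient cannot show a delay

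*SAP*

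**What the plan says.** In the SAP (Analyses of primary outcomes, Aim 2), Mixed Model Regression is used "to assess the long-term effects of the CHAMP intervention on improving the three outcome measures: motor performance, perceived physical competence and physical activity". The analysis is said to give "estimates of the long-term longitudinal intervention effect by adjusting for confounding factors that include sex and age". The protocol (E. Statistical Analysis, Objective 1, Aim 2) has the same sentence but names only sex.

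The SAP then continues: "For physical activity and BMI, we will test for a possible delay before any significant change". The method is "adding time-lagged covariates related to behaviour changes in the regression analysis". The protocol plans the same test for PA alone, "by adding time-lagged covariates related to behavior changes in the regression analysis". Neither document names the covariates, gives the lag, or says whether this is a separate model from the one that yields the long-term effect.

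The following sentence in the SAP plans to "conduct exploratory analyses to test interaction effects to understand potential modified intervention effects by different levels of behaviour changes".

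Both documents also plan intervention-by-time interactions in Aim 2. Both fit growth curves to find when the effect is stronger, and both place mediation under Aim 3.

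**The concern.** A covariate that records behaviour change needs a measurement after baseline, so it is a post-randomisation variable. CHAMP is designed to change these behaviours, so the covariate lies on the path from arm to outcome. Once it is in the model, the arm coefficient is what remains of the effect at that visit after the part associated with earlier behaviour has been taken out. Common causes of earlier and later behaviour can bias that remainder further.

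Delay means that the arm effect is small at an early visit and larger at a later one. That is a statement about two total effects, and a coefficient that mixes them cannot answer it. Hypothesis 2 expects a sustained benefit. If Hypothesis 1 is also true and CHAMP has already raised activity by month 9, this model would show a sustained effect as smaller than it is and could suggest fading.

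The modification analysis has a related weakness. Levels of behaviour change define groups that form after randomisation, so differences in arm effect between them have no causal reading.

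**Working it through.** **Inputs from the protocol** (Sample Size, Power Analysis and Sample Attrition): difference 12.1 min MVPA/day, SD 27, 90% power, alpha 0.05 (taken as two-sided), 212 evaluable children (106 per arm).

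**Assumptions not in the documents:**
- The lagged covariate is MVPA at the previous visit.
- The within-arm correlation r between visits is 0.3, 0.5 or 0.7.
- The SD is 27 at both visits.
- There are two visits, with no clustering and no random effects.

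**Step 1. Reproduce the plan's figure.** n per arm = 2 × (1.960 + 1.282)² × 27² / 12.1² = 104.6, so 105 per arm (210 in total). With the t distribution, power is 0.898 at 105 and 0.901 at 106 per arm, so the stated 212 reproduces. It sizes the immediate effect. The documents give no figure for the lagged-covariate model.

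**Step 2. What the arm coefficient becomes.** Let d1 and d2 be the arm effects at the earlier and later visit. Regress the later outcome on arm and a lagged covariate. The arm coefficient is d2 − b × dx, where dx is CHAMP's effect on the covariate and b is the within-arm slope of the outcome on it. For lagged MVPA with equal SDs, b = r and dx = d1, so the coefficient is d2 − r × d1.

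**Step 3. Put the numbers in** (min/day).

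| Pattern | d1 | d2 | r = 0.3 | r = 0.5 | r = 0.7 |
|---|---|---|---|---|---|
| Sustained | 12.1 | 12.1 | 8.47 | 6.05 | 3.63 |
| Building | 6.05 | 12.1 | 10.29 | 9.08 | 7.87 |
| Pure delay | 0 | 12.1 | 12.1 | 12.1 | 12.1 |
| Smaller pure delay | 0 | 6.05 | 6.05 | 6.05 | 6.05 |
| Halving | 12.1 | 6.05 | 2.42 | 0.00 | −2.42 |

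A simulation of 400,000 children agreed: 8.46, 6.09 and 3.55 for the sustained pattern, and 12.10, 12.15 and 12.03 for the pure delay of 12.1.

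At r = 0.5 the sustained 12.1 and the delayed 6.05 share one coefficient. A halved but real benefit shows as zero.

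**Step 4. Power of that arm term under a sustained effect.** The residual SD is 27 × √(1 − r²), which is 25.76, 23.38 or 19.28. Power at 106 per arm is Φ(coefficient / (residual SD × √(2/106)) − 1.96), which is 0.67, 0.47 or 0.28. Without the lagged covariate it is Φ(12.1 / (27 × √(2/106)) − 1.96) = 0.90.

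**Step 5. Compare with a visit contrast.** The contrast d2 − d1 between visit-specific arm effects is 0 for the sustained pattern, +6.05 for the smaller delay and −6.05 for halving. It separates the three patterns, and its expected value does not depend on r.

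**The case against.** The strongest reply is that the SAP describes the Aim 2 estimate first, adjusted for sex and age, and brings in the lagged covariates afterwards for another purpose. A reader might infer that the reported sustained effect will itself be reduced. The documents do not say that the lagged model supplies that estimate, so this is a risk from unclear wording and not a stated fact.

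Other limits also stand:
- The delay test covers physical activity and BMI only. Motor performance, perceived competence and the Aim 1 comparison are untouched.
- A reader might infer that late effects are inflated. They are not: with d1 = 0 the coefficient equals d2. A late effect only looks large beside a sustained one that has shrunk.
- The coefficient is the change in arm effect since the previous visit only if r = 1.
- Lagged MVPA is an assumed covariate. With lagged motor or perceived competence, the loss depends on CHAMP's effect on that variable and on its slope with the outcome.
- The modification analysis is labelled exploratory and does not enter the main estimate.
- Intervention-by-time terms and growth curves are already planned, so conclusions on timing need not rest on the lagged model.

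These points narrow the concern but leave the stated delay test unsound. The general form d2 − b × dx holds for whichever lagged behaviour is chosen. It equals the total effect only if CHAMP did not change that behaviour or the behaviour is unrelated to the outcome.

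**Conclusion.** The concern holds for the delay test on physical activity and BMI. Its arm coefficient is not the total effect at the visit and cannot separate a sustained effect from a delayed one. The defect is in the method as well as in the detail given, because defining the covariates would not turn the model into a test of delay.

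If the covariate is lagged MVPA, 30%, 50% or 70% of a sustained effect is removed at r of 0.3, 0.5 or 0.7, and nothing is removed from a pure delay. These sizes rest on the assumed covariate, the assumed correlations, equal SDs and no clustering.

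Whether the main Aim 2 estimate is affected cannot be settled from the documents. It is safe if it comes from a separate model, and the SAP should say so.

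**What to change.** In the SAP's Aim 2, and in the matching protocol section:

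1. State that the Aim 2 effect model contains arm, time, arm-by-time and baseline covariates only.
2. Test delay, for physical activity and for BMI if it is kept, from that same mixed model. Report the arm effect at each follow-up visit and its contrast with the month 9 arm effect, with 95% confidence intervals.
3. Move any lagged-behaviour model to the Aim 3 mediation analysis, or label it exploratory and not a test of delay. In either case define the variables and the lag.
4. State that effect modification by behaviour change is non-causal, because its groups form after randomisation.

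The cost is wording only. The intervention-by-time terms and the mediation analysis are already planned, and no new data, visits or participants are needed.
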